11.2 Analysis Methodology for the Exploratory Endpoints

11.2.1 Estimand for the Number of Good Days (Week 1-4, 1-12, and 1-24) and Exploratory Endpoints

A summary of the intercurrent events that will be addressed and the estimand attributes can be found below.

The estimand is the difference in the mean weekly number of good days within each specified time interval between eptinezumab compared to other advanced preventive therapies (erenumab, fremanezumab, galcanezumab, or onabotulinumtoxinA) in adults with migraine on concomitant acute migraine therapy who have failed ≥ 2 prior oral preventive therapies and who are naïve to advanced migraine therapy based on a treatment policy strategy in which patients are analyzed according to the randomized group and are included in the analysis regardless of discontinuation or switching of the index migraine therapy during the follow-up period.

Intercurrent events that will be addressed include:

- Discontinuing the index preventive migraine medication with or without initiation of a new preventive therapy (i.e., a treatment switch).
- Withdrawal from the study due to lack of efficacy, adverse event, participant request, physician request, or loss to follow-up.
- Interruption or termination of infusions.

Attributes of the estimand for the number of good days include:

- The index treatment of interest is eptinezumab (100 mg or 300 mg) compared to other advanced preventive therapies (erenumab 70 mg or 140 mg, fremanezumab 225 mg or 675 mg, galcanezumab 120 mg, and onabotulinumtoxinA 155 units)
- The population is all patients with migraine who fulfil the inclusion and exclusion criteria.
- The primary endpoint of interest is the mean number of good days across weeks 1-12 after randomization
- The population-level summary is the mean difference between eptinezumab and other advanced preventive therapies for the endpoint

Estimands for the remaining exploratory endpoints can be formulated similarly to the estimand for the number of good days described above.

EQ-5D (weeks 1-4, 1-12, and 1-24)

- The endpoint to be obtained is the weekly EQ-5D score in each specified time interval
- The population level summary is the difference in mean weekly EQ-5D score in patients on eptinezumab relative to advanced migraine therapies in each time interval

PI-MBS (weeks 1-4, 1-12, and 1-24)

- The endpoint to be obtained is the weekly most bothersome symptom and associated severity

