11.2.2 Analysis of the Exploratory Endpoints

The analysis of exploratory endpoints assumes that we have $\leq 10\%$ of patients with at least one missing outcome value. A complete case analysis will be used as a preliminary approach to establish the “baseline” results prior to using a mixed model for repeated measures (MMRM) or multiple imputation to account for missing values.

Number of good days (weeks 1-4, 1-12, and 1-24)

The weekly difference in mean number of good days will be estimated using a MMRM. The model will include the following independent variables:

- Week as a factor (week 1, week 2, week 3, week 4...week n)
- Treatment indicator (eptinezumab vs other advanced therapies)
- Interaction of treatment and week (i.e., treatment*week 1...treatment*week 2...treatment*week n)
- A vector of covariates identified to be significantly different between treatment groups after randomization.

We will assume that residuals are normally distributed, and we will also assume an unstructured covariance structure of the residuals. The Kenward-Roger approximation will be used to estimate standard errors. The hypothesis tested will be that the interaction term of treatment and week is significantly different from zero using a two-sided test at $p < 0.05$. The

population level summary will be the difference in mean number of good days at weeks 1-4. The analysis will also be conducted for weeks 1-12 and 1-24. If the model fails to converge, then other covariance structures will be utilized.

EQ-5D score (weeks 1-4, 1-12, and 1-24)

The weekly difference in the EQ-5D score will be estimated using a MMRM. The model will include the following independent variables:

- Week as a factor (week 1, week 2, week 3, week 4...week n)
- Treatment indicator (eptinezumab vs other advanced therapies)
- Interaction of treatment and week (i.e., treatment*week 1...treatment*week 2...treatment*week n)
- A vector of covariates identified to be significantly different between treatment groups after randomization.

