We will assume that residuals are normally distributed, and we will also assume an unstructured covariance structure of the residuals. The Kenward-Roger approximation will be used to estimate standard errors. The hypothesis tested will be that the interaction term of treatment and week is significantly different from zero using a two-sided test at $p<0.05$. The population level summary will be the difference in mean EQ-5D score at weeks 1-4. The analysis will also be conducted for weeks 1-12 and 1-24. If the model fails to converge, then other covariance structures will be utilized.

HCRU (weeks 1-4, 1-12, and 1-24)

The difference in cumulative mean HCRU will be estimated using a negative binomial model. The analysis will be stratified by type of HCRU (i.e., outpatient, inpatient hospitalization, emergency department/urgent care visits, and migraine-specific medications such as triptans). Independent variables will include a treatment indicator (eptinezumab vs other advanced therapies) and a vector of covariates identified to be significantly different between treatment groups after randomization. The hypothesis tested will be that the treatment term is significantly different from zero using a two-sided test at $p<0.05$. The population level summary will be the relative difference in mean HCRU at weeks 1-4. The analysis will also be conducted for weeks 1-12 and 1-24. If there are a substantial number of observations with a value of zero HCRU, then a zero-inflated negative binomial model will be explored.

HIT-6 change from baseline score (month 1, 3, and 6)

The mean HIT-6 change from baseline score will be estimated using a mixed model for repeated measures (MMRM). The model will include the following independent variables:

- Month as a factor (Baseline month 0, month 1, month 3, and month n)
- Treatment indicator (eptinezumab vs other advanced therapies)
- Interaction of treatment and month (treatment*baseline...treatment*month 1...treatment*month n)

- A vector of covariates identified to be significantly different between treatment groups after randomization.

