11.2.6 Sensitivity Analyses of the Exploratory Endpoints

Number of good days (weeks 1-4, 1-12, and 1-24), EQ-5D score (weeks 1-4, 1-12, and 1-24), HIT-6 change from baseline score (month 1, 3, and 6), and MIDAS change from baseline score (month 3 and 6)

To test the robustness of the results with respect to missing data, the missing data will be imputed using multiple imputation by chained equation assuming data is missing at random.¹ First, the proportion and pattern of missing outcome values will be evaluated, and descriptive statistics of variables with missing values will also be evaluated. Additionally, among outcome variables with missing data, the association of missingness with other variables will be measured. Missing values will be imputed using fully conditional specification imputation in which each variable with missing values is imputed using regression (type of regression dependent on the variable distribution). Imputation models will be specified to include all analytic variables and additional variables that are associated with missingness. A minimum of 20 imputed datasets will be generated.² Trace plots for continuous variables and tabulations for categorical variables of the imputed datasets will be evaluated to assess the validity of imputations methods. Methods to “penalize” missing values will also be explored. Only observations in the eptinezumab group will be used to impute missing data in patients randomized to eptinezumab, and only observations in the comparator arm will be used to impute missing data in patients randomized to the comparator arm.

A mixed model with repeated measures (MMRM) will be used to evaluate the association between treatment and patient reported outcomes and a generalized linear model (log link and gamma distribution) will be used to evaluate the association between treatment and HCRU across the imputed datasets. Coefficients and standard errors obtained from each imputed dataset will be pooled and combined for inference using PROC MIANALYZE in which regression coefficients are averaged across imputations and standard errors are estimated to incorporate uncertainty within imputations and between imputations.¹ The hypothesis tested will be that the treatment term is significantly different from zero using a two-sided test at $p<0.05$. The population level summary will be the difference in means at each specified time interval.

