As would be expected in a pragmatic trial, the sample size of EVEC (100 persons per arm) is a function of the project budget and timeliness. In [Panel 6](#) we illustrate the expected power based upon the assumptions developed from PROMISE 1 and 2. We have highlighted the 100 per arm for the PROMISE 2 effect size. If, as expected, we meet the PROMISE 2 assumptions, we will have at least 72% power to demonstrate a standardized effect of 0.45. Given that we believe that the effect size will be larger in EVEC than observed in PROMISE 2, even as we pool patients with episodic and chronic migraine, we expect to have a practical power in excess of 80% to find a difference between eptinezumab and the other advanced preventive medications with an alpha of 0.05.

16 Statistical Software

Analyses will be conducted using SAS[®], Version 9.4 or later and R[®], Version 4.2.1 or later.

17 Changes to Analyses Specified in the Protocol

N/A

18 Details on Data Handling

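### The multiple-imputation sensitivity analysis tests a different and under-specified term from the main mixed model, so its p-value cannot be read against the main p-value

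*SAP*

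**What the plan says.** **Main analysis (SAP 11.2.2).** Good days, EQ-5D, HIT-6 and MIDAS each get a mixed model for repeated measures with time as a factor, a treatment indicator and treatment-by-time. For good days and EQ-5D, "The hypothesis tested will be that the interaction term of treatment and week is significantly different from zero using a two-sided test at" p<0.05. HIT-6 and MIDAS have the same sentence with month in place of week. The summary to be reported is a difference in means over weeks 1-4, 1-12 and 1-24, or a difference in change at the named months. The estimand in 11.2.1 agrees: "The population-level summary is the mean difference between eptinezumab and other advanced preventive therapies for the endpoint".

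**Sensitivity analysis (SAP 11.2.6).** Its purpose is "To test the robustness of the results with respect to missing data", for the same four endpoints. It names a mixed model for repeated measures without listing terms, factor coding or a reference level. Then: "Coefficients and standard errors obtained from each imputed dataset will be pooled and combined for inference using PROC MIANALYZE". The test follows: "The hypothesis tested will be that the treatment term is significantly different from zero using a two-sided test at" the 0.05 level. The next sentence gives the summary as the difference in means at each specified time interval.

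**Software (SAP 16).** Both SAS and R are allowed. PROC MIANALYZE, named in 11.2.6, is a SAS procedure.

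**The concern.** A missing-data sensitivity analysis is informative when only the handling of missing values changes. Here the tested hypothesis changes too: treatment-by-time in the main analysis, the treatment term in the sensitivity analysis. If one is significant and the other is not, the reader cannot tell whether missing data or the switch of hypothesis caused it. If both are significant, that agreement is not evidence of robustness either.

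The second problem is what the treatment term means. In a model that keeps treatment-by-time, a reference-coded treatment coefficient is the arm difference at the reference time only. A reader would naturally take its p-value as belonging to the interval difference in means stated in the next sentence, and it need not.

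**Working it through.** The SAP gives no figure for this point, so there is none to reproduce. The check is algebra, followed by an illustration under assumed values.

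**1. What the coefficient is.** Write the arm difference at time w as Δ_w = τ + γ_w, where τ is the treatment coefficient and γ_w the interaction. Reference coding sets γ_ref = 0, so τ = Δ_ref. The interval summary is the mean of the Δ_w, that is τ + mean(γ_w). The two agree only when the mean of the γ_w is zero, for example under a constant effect. The default reference is the last level in SAS and the first in R.

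**2. Noise-free check over 12 weeks (assumed patterns).**

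| Arm difference | τ, first level as reference | τ, last level as reference | Sum-coded, or interaction dropped | Interval mean |
|---|---|---|---|---|
| Fading 1 to 0 | 1.0 | 0.0 | 0.5 | 0.5 |
| Growing 0 to 1 | 0.0 | 1.0 | 0.5 | 0.5 |
| Constant 0.6 | 0.6 | 0.6 | 0.6 | 0.6 |

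For HIT-6, with assumed differences in change of -2, -3 and -4 at months 1, 3 and 6, last-level coding returns -4.0. That is month 6 only; months 1 and 3 are not tested.

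**3. The hypotheses under each reading of 11.2.6.**
- *Interaction kept, reference coding:* Δ_ref = 0. This differs from the 11.2.2 test (all Δ_w equal) and from the interval mean.
- *Interaction dropped, or sum-coded/Type 3 effect:* average Δ = 0. This is the kind of quantity 11.2.6 reports, but it still differs from the 11.2.2 test.

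No reading makes the sensitivity test the same as the main test.

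**4. Power for a constant benefit (assumed values).** Take 100 per arm, weekly SD 2, intraclass correlation ICC, K weeks and no missing data.
- SE of the interval-mean difference = 2·√(ICC + (1 − ICC)/K)·√(2/100), when within-person errors are otherwise independent.
- SE of a single-week difference = 2·√(2/100) = 0.283.
- Benefit with 80% power on the mean: d = (1.96 + 0.84)·SE_mean.
- Single-week power ≈ Φ(d/0.283 − 1.96).

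| ICC (K = 12) | SE_mean | d (days/week) | Single-week power |
|---|---|---|---|
| 0.3 | 0.169 | 0.474 | Φ(−0.28) = 39% |
| 0.5 | 0.208 | 0.583 | Φ(0.10) = 54% |
| 0.7 | 0.241 | 0.675 | Φ(0.43) = 67% |

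Simulations that also varied K (12 or 24) and within-person AR(1) correlation (0 or 0.5) gave 35-49%, 51-60% and 64-69% at the three ICC values, so about 35-69% overall.

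**5. Benefit fading linearly to zero, same interval mean.** At the last week Δ = 0, so a last-week coefficient rejects at its nominal rate. Simulation gave 4-6%, against 80% for the interval mean.

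**6. Can the interval means still reveal a missing-data problem?** A separate simulation (100 per arm, 12 weeks, true difference 0.5) deleted the lowest values in one arm, from none at week 1 up to 20% at week 12. No imputation was run. From complete to observed data, the interval-mean difference went from 0.499 to 0.128, the week-12 difference from 0.499 to −0.193, and the week-1 difference stayed at 0.499. The interval mean shows the problem; a first-week coefficient would not.

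**The case against.** The strongest defence is that the sentence is loose shorthand. The same paragraph of 11.2.6 also covers a generalized linear model for resource use, where testing the treatment term is ordinary wording, and the next sentence names the interval difference in means. If the interaction was meant to be dropped, or a Type 3 main effect intended, the tested quantity is an average effect in line with that summary. This stands in part: the single-time reading is one possibility, not something the text states. It does not rescue the comparison with 11.2.2, which tests the interaction under any reading.

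A reader might infer three stronger points that the documents do not support.

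- *That the HIT-6 and MIDAS test is a test at baseline.* The time factor does list month 0 ("Month as a factor (Baseline month 0, month 1, month 3, and month n"), but that reading needs first-level coding, which the SAP does not state and which PROC MIANALYZE does not suggest. Both endpoints are changes from baseline, so the month-0 value is zero by definition and there is no imbalance to test.
- *That the sensitivity analysis cannot show whether missing data changed the result.* Section 11.2.6 also reports interval mean differences. These can be set against the 11.2.2 summaries, and step 6 shows that such a comparison can reveal a shift.
- *That frequent disagreement between the two tests under a constant benefit measures this fault.* Such disagreement largely reflects the interaction test's lack of power against a constant effect, which is a separate matter about 11.2.2.

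It is also fair to say that all objectives are exploratory (Protocol 3.3) and that no decision rule depends on the sensitivity p-value. That limits the consequence, but the SAP still prespecifies the test at p<0.05.

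**Conclusion.** Wrong as written. That the main and sensitivity tests address different hypotheses follows from the SAP's wording alone and needs no assumption. That the pooled coefficient describes a single time level is conditional on reusing the 11.2.2 terms with reference coding; 11.2.6 neither states nor excludes this.

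Under that condition, power for a sustained benefit falls from 80% to about 35-69%, and to about 5% for a benefit gone by the last week under last-level coding. These sizes rest on an assumed weekly SD of 2, ICC of 0.3-0.7, the stated effect shapes, 100 per arm and complete data. They illustrate the consequence of that reading and are not evidence for it. The fault lies in the stated test and its p-value; the interval mean differences in 11.2.6 remain usable.

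**What to change.** In SAP 11.2.6, replace the sentence on the treatment term as follows.

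- Fit the same model terms as 11.2.2 in each imputed dataset.
- In each dataset, estimate the least-squares-mean contrast already named as the population-level summary. For good days and EQ-5D this is the equally weighted average of the weekly arm differences over weeks 1-4, 1-12 and 1-24. For HIT-6 and MIDAS it is the arm difference in change at each named month.
- Pool that contrast and its standard error in PROC MIANALYZE, and state that raw model coefficients are not pooled for inference.
- In 11.2.2, obtain the identical contrast from the main mixed model.
- Judge robustness by comparing the two estimates and their 95% confidence intervals.

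A contrast defined this way does not depend on the reference level or the package. The cost is a few lines of SAP text and one ESTIMATE or LSMESTIMATE statement (or the R equivalent) per model. It needs no new data and no protocol amendment; the only downside is slightly more programming.

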11.2.7 Supplementary Analyses of the Exploratory Endpoints

The correlation between migraine days and patient reported outcomes will be evaluated visually by plotting the average number of weekly migraine days versus average weekly values of the PI-MBS severity, number of good days, and EQ-5D across the 24-week follow-up period based on the entire cohort. Weekly correlation values will be calculated using Spearman’s rank correlation and plotted across time.

11.2.8 Covariate Investigation and Subgroup Analyses of the Exploratory Endpoints

Although patients are randomized to eptinezumab and advanced therapies, randomization may not produce balanced groups. Baseline covariates listed below will be compared across the treatment groups using descriptive statistics. Significant differences will be tested using the t-

test or the Mann-Whitney test for continuous variables and chi-square test for categorical variables ([Appendix I](#)).

Baseline covariates include:

- Demographic variables
 - Age
 - Sex
 - Marital status
 - Race/ethnicity
 - Zip code
 - Highest education level attained
 - Current employment status
- Clinical variables
 - eDiary compliance
 - Number of migraine days in each of the past three months (MMDs)
 - Previous use of oral preventive medications
 - Migraine symptoms experienced in the seven days prior to enrollment
 - Migraine history (including age at time of first attack and classification of migraine as CM, EM, and MOH)
 - Migraine related medication history
 - Vital signs (height, weight, blood pressure, pulse, respiration)
 - All current medications being taken (including prescription, OTC, vitamins/supplements, vaccinations)
 - Medication allergies
 - Medical and psychiatric history
 - Cardiac history
 - Family medical history of migraines (parents and siblings)
 - Use of tobacco or vaping products, or any other nicotine product
 - Perceived stress scale

No subgroup analyses are planned.

12 Safety Analyses

Adverse events (AEs) will be collected throughout the 6-month study period. Analyses of adverse events will be based on the APTS, and events will be reported according to the therapy the patient received (i.e., not the randomized group).

All AEs will be coded according to the MedDRA version 24.0 or higher. The incidence of AEs occurring in the 6-month study period will be analyzed using descriptive statistics by therapy received. Given sufficient sample size, AEs may also be evaluated by dose received to evaluate any AE trends by dose.

Adverse events will be recorded according to MedDRA system organ class and preferred term by therapy group and classified as pre-treatment adverse events (an adverse event that starts on or after the date the patient signed the Informed Consent Form and prior to the date and time of first dose of therapy) or treatment-emergent adverse events (TEAE; an adverse event that starts or increases in intensity on or after the date and time of first dose of therapy). Only TEAEs will be reported and will be tabulated as:

- Any AEs
- AEs probably related to the therapy received stratified by AE
- Severe AEs stratified by AE
- AE leading to treatment discontinuation stratified by AE
- Serious AE stratified by AE
- Serious AE probably related to the therapy received by AE
- Serious AE leading to treatment discontinuation stratified by AE
- Fatal AE
- Overall AEs
 - Any SAE
 - Any AE probably related to the therapy received
 - Any Severe AE
 - Any AE leading to treatment discontinuation
 - Any serious AE
 - Any serious AE probably related to the therapy received
 - Any serious AE leading to treatment discontinuation
 - Fatal AE

13 Data Reviews

Data quality is controlled throughout the study by study-specific edit checks programmed within the software platforms used to collect data (eCaseLink and eCaseLinkMe).

Edit checks are separated into the following categories:

- Programmed edit checks primarily checks programmed within the EDC system that allow for data to be checked in real time during the data entry process, and which assist sites during data entry. These checks may be divided into:
 - Database Check: The corresponding data field limits the entry to a specific format (e.g. time in “HH:MM” [hours:minutes]).
 - Programmed Soft Check: This check category allows a confirmation of the discrepant information and subsequent manual closing of the discrepancy by Xcenda.
 - Programmed Hard Check: This check category requires a correction of the entered value to close the discrepancy.
- Manual edit checks: Checks that are not pre-programmed within the EDC system and are performed by appropriate Lundbeck and/or Xcenda study personnel. Manual checks may

result in the need for manual queries to be recorded by Xcenda within the EDC system for site response and/or data correction.

It is the responsibility of Xcenda to check on a regular basis whether additional edit checks are necessary to achieve final clean database with an acceptable error rate. All additional checks following deployment of the EDC system to the LIVE environment have to be approved by Lundbeck prior to implementation. Subsequent changes to the edit checks after first version release are tracked within the data dictionary.

Data recorded within eCaseLinkMe will not be queried by Xcenda, however, site study personnel will be trained to review the ePRO data prior to their monthly touchpoint with the patient in order to address any data entry errors or missing data moving forward. Patients will not have the ability to modify data once it has been submitted within eCaseLinkMe. Data listings may be generated in order to inform the study team of erroneous, implausible, or missing data. Findings from data listings may be shared with study sites in order to retrain patients on the data entry process and requirements. Data will be checked in real time via pre-programmed edit checks that will assist the patient during the data entry process. Edit checks will be detailed in the data dictionary.

Lundbeck will conduct manual data reviews based on weekly data transfers from Xcenda which include but are not limited to:

- eCaseLink
 - Descriptive statistics to evaluate randomization group, baseline demographics, medical history, concomitant medications, adverse events, and treatment administration. Missing data will be flagged and monitored. Consistent missing data will be escalated to Xcenda.
- eCaseLinkMe
 - Descriptive statistics to evaluate daily headache status and associated symptoms, and trends in patient reported outcomes. Missing data will be flagged and monitored. Consistent missing data will be escalated to Xcenda.

14 Interim Analyses

No interim analyses are planned.

15 Sample Size

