### **Assessment of Causal Relationship**

The investigator must assess the *causal relationship* between the adverse event and the IMP using the following definitions, and record it on the *Adverse Event Form and the Serious Adverse Event Form (if applicable)*, in the eCRF:

- Probable – the adverse event has a strong temporal relationship to the IMP or recurs on rechallenge, and another etiology is unlikely or significantly less likely.
- Possible – the adverse event has a suggestive temporal relationship to the IMP, and an alternative etiology is equally or less likely.
- Not related – the adverse event has no temporal relationship to the IMP or is due to underlying/concurrent disorder or effect of another drug (that is, there is no causal relationship between the IMP and the adverse event).

An adverse event is considered causally related to the use of the IMP when the causality assessment is *probable* or *possible*.

For pre-treatment adverse events, a causality assessment is not relevant.

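### All four relatedness outputs in SAP section 12 are limited to probably related events, so the related AE and serious AE rates as Protocol 10.1.2 defines them are never tabulated

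*SAP*

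**What the plan says.** Protocol section 10.1.2 (Assessment of Causal Relationship) asks the investigator to record one of three grades on the AE form. Two of them are separately defined degrees of relatedness: "Probable – the adverse event has a strong temporal relationship to the IMP or recurs on rechallenge", and "Possible – the adverse event has a suggestive temporal relationship to the IMP, and an alternative etiology is equally or less likely". The third is not related. The section then gives the rule for combining them: "An adverse event is considered causally related to the use of the IMP when the causality assessment is" either probable or possible.

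SAP section 12 (Safety Analyses) reports treatment-emergent events only and lists the tables. Four concern relatedness:

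- by term, all AEs: "AEs probably related to the therapy received stratified by AE"
- by term, serious AEs: "Serious AE probably related to the therapy received by AE"
- overall summary, all AEs: "Any AE probably related to the therapy received"
- overall summary, serious AEs: "Any serious AE probably related to the therapy received"

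The other outputs (any AE, severe, serious, leading to discontinuation, fatal) carry no causality condition unless they are among these four. SAP section 17, on changes from the protocol's analyses, is marked as not applicable. Protocol section 16.3.1 says that AE and adverse drug reaction data will be tabulated, and sets no limit to probable events.

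**The concern.** In this trial *probable* is a recorded data value with its own definition, and so is *possible*. A programmer who reads the SAP literally will filter on the first value and drop the second. All four lines carry the same wording, so this does not look like a slip in one row.

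SAP Panel 1 makes the safety and tolerability of eptinezumab a stated objective, and the safety analysis is descriptive, so the tables are the safety result. A reader of the study report who finds only a probably related row may take it for the related-event rate as the protocol defines it. This applies to serious events too: a serious AE graded possible is causally related under the protocol but would appear in neither related serious AE output.

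**Working it through.** No sample size, power or alpha figure bears on this point and the plan gives no figure to reproduce. The check is a comparison of the two texts.

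**Step 1. Map the grades to the rule and to the outputs.** Inputs: the three grades and the combining rule (Protocol 10.1.2) and the list of outputs (SAP section 12), for treatment-emergent events.

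| Grade on the AE form | Related under Protocol 10.1.2? | In the four SAP relatedness outputs? | In any AE, and in the severe, serious, discontinuation and fatal outputs where it qualifies? |
|---|---|---|---|
| Probable | yes | yes | yes |
| Possible | yes | no | yes |
| Not related | no | no | yes |

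The documents disagree in the second row only, and they do so in 4 of 4 relatedness outputs.

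**Step 2. Look for text that would reconcile them.** SAP section 12 does not define probably related, has no line for possibly related, and has no line for related without a qualifier. SAP section 17 declares no departure. Protocol 16.3.1 does not narrow the definition. Protocol 10.1.1 defines no separate category of adverse drug reaction that could stand in for it, so the rule in 10.1.2 is the only one available to say which AEs count as related. Nothing reconciles the two texts.

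**Step 3. Size.** Let *s* be the share of related events that are graded possible. The relatedness outputs then omit a share *s* of related events. Neither document gives *s*. For a purely hypothetical 20 related events:

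| *s* (assumed) | Omitted = 20 × *s* | Shown |
|---|---|---|
| 0% | 0 | 20 |
| 25% | 5 | 15 |
| 50% | 10 | 10 |
| 75% | 15 | 5 |

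This restates the assumption and is not an estimate. Nor does it carry over to incidence by participant, which is what an *any related AE* row would normally show. There, the omitted participants are those whose related events were all graded possible. Take *s* = 50%, that is 10 probable and 10 possible events. If the same 10 participants each have one of each, no participant is missed. If one participant has all 10 probable events and 10 others have one possible event each, 10 of 11 are missed. The participant-level shortfall can therefore lie below or above *s*.

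**The case against.** Four arguments can be made for leaving the text alone.

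*The table label is honest.* A table headed probably related reports what its heading says, and no event is miscounted. This stands as far as it goes. The defect is an omission and a mismatch of definitions: the rate that the protocol defines is not produced anywhere, and the narrower one stands in its place without comment.

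*The authors may simply have meant related.* They may have. The SAP does not say so, and because *probable* is a coded grade the loose reading cannot be assumed. That ambiguity is a reason to settle the wording before the tables are programmed.

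*The events are reported elsewhere.* This stands, and it limits the point. A reader might infer that events graded possible vanish from the safety report, or that all safety tables are restricted. The documents do not support that: the all-AE output and the severe, serious, discontinuation and fatal outputs are not filtered by causality.

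*The consequence is small.* The study is exploratory, the safety analysis is descriptive, and the SAP safety endpoint is reported adverse effects in general. A reader might also infer that safety oversight during the trial is weakened. It is not: reporting of serious AEs within 24 hours (Protocol 10.3 and 10.4) and the definition of a suspected unexpected serious adverse reaction (Protocol 10.1.1) do not depend on the SAP tables. What is affected is the end-of-study summary.

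**Conclusion.** Wrong as written. The SAP's four relatedness outputs conflict with the protocol's definition of causally related, and the departure is undeclared. The effect is confined to those four outputs: treatment-emergent events graded possible are absent from them, and the protocol-defined related AE and related serious AE rates go unreported.

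The size is unknown, and is zero only if no event is graded possible. A reader might be tempted to say that the related rate will come out at about half its true value. The documents give no split between the two grades from which to derive that or any other fraction.

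The conclusion rests on one assumption, that the SAP wording will be programmed literally. If it is not, the conflict in the text remains but the tables may come out right.

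**What to change.** In SAP section 12, replace the restriction in all four lines with related, defined as probable or possible per Protocol 10.1.2. Probable and possible may be shown as sub-rows, which keeps the information that the present wording would give.

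If the narrower definition is deliberate, keep it as an additional row beside the protocol-defined one, and declare it with its reason in SAP section 17.

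The cost is a wording change in the SAP and the matching table shells. The causality grade is already collected for each event on the AE form (Protocol 10.1.2 and 10.3), so there is no change to data collection, visits or sample size.
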